10 SAFETY TABLES, PARTICIPANT LISTINGS, AND FIGURES

10.1 List of Tables

- Enrollment Report
- Demographics and Vaccination Frequencies
- Overall Protocol Status
- Maximum Local and Systemic Reactogenicity Summaries
- Adverse Experiences by Body System and Severity By Decreasing Frequency
- Adverse Experiences by Preferred Term and Severity By Decreasing Frequency Includes Severe, Life-threatening or Fatal Experiences Only
- Adverse Experiences by Preferred Term and Severity By Decreasing Frequency Includes Experiences of All Severities
- Adverse Experiences by Preferred Term and Relationship to Study Product By Decreasing Frequency – Includes Related Experiences Only
- Expedited Adverse Experiences (EAEs) Reported to the Regulatory Support Center (RSC)
- Medically Attended Adverse Events (MAAE)
- Pre-Enrollment Procedure-Related Events
- Pregnancy Listing

Additional tables included in the FSR for Safety:

- Social Impact Summary
- End of Study Diagnostic ELISA Testing Results
- Local Lab Value Summary Statistics
- Local Laboratory Values Meeting Grade 1 AE Criteria or Above

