The team has also considered whether to include temporal limits on platelets/INR, and a temporal requirement to abstain from NSAID/aspirin use prior to leukapheresis and has decided not to include these as restrictions (48). We note that the trial eligibility criteria exclude persons with bleeding disorders (eg, factor deficiency, coagulopathy, or platelet disorder requiring special precautions (see Section 5.1.2). Assessment of patients post leukapheresis found the most frequent side effect (39%) was paresthesia due to citrate-related hypocalcemia, managed with oral calcium supplements and/or slower rates. No bleeding occurred (52). The study team conclude that adverse reactions with leukapheresis are similar to those reported for conventional PBMC collections. Routine measurement of INR has demonstrated no ability to identify patients who are at risk of periprocedural bleeding even with higher risk procedures such as placement of central venous catheter (47).

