FNA of lymph nodes: Can sometimes cause pain, bruising, and bleeding at the site where the needle is inserted. Similar to any procedure where a needle is inserted into the skin (such as vaccination, as described above), there is a rare risk of localized infection. Rarely, the local anesthetic can cause arm numbness or weakness.

Risks during pregnancy: Because possible effects of the study vaccine on a fetus or nursing infant are unknown, persons assigned female sex at birth who have reproductive potential will be tested for pregnancy at screening and prior to administration of each dose of the study vaccine. Such persons will be asked to notify the site immediately if they suspect or learn they are pregnant during this study. In case of pregnancy, participants will continue to be followed for safety and the participant will not receive any additional vaccinations. The participant will be contacted about the outcome of a pregnancy that begins during the study.

Other risks: The medical tests performed as part of this research protocol may result in new diagnoses or abnormal values without clinical significance ("false positives"). Depending on the medical findings and consequences of being provided with the results of these tests, the study participant may view this as either a risk or a benefit. Any such information will be shared and discussed with the participant and, if requested by the participant, may be forwarded to their primary health care provider for further workup and management.

Participants in this study risk experiencing discrimination or other personal problems that may result from study participation itself: these types of risks are known collectively as "negative social impacts." The HVTN CRS is obliged to provide advocacy for and assistance to participants regarding these negative social impacts associated with the vaccine trial. If HVTN CRS staff have questions regarding ways to assist a participant dealing with a negative social impact, a designated HVTN Core representative can be contacted.

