The first 5 participants enrolled in the study will be assigned to Group 1. The PSRT will convene to review safety data recorded from these 5 participants through the visit scheduled 2 weeks post–first vaccination. If the PSRT determines that it is safe to proceed with enrollment, the remaining participants (approximately 40) will be randomized between Groups 1, 2, and 3.

Participants will be monitored for up to 18 months postenrollment. We anticipate that the study will take at least 22 months to be completed.

Participants will be evaluated for safety and immune responses through blood collection, lymph node FNA, and leukapheresis at specified timepoints throughout the study.

The study will target enrolling at least 50% of participants willing to undergo FNA in Groups 2 and 3. Participants enrolled in Group 1 will not undergo FNA. See Sections 1.5 and 2.11 for details.

Primary and secondary objectives will seek to characterize and compare immunogenicity endpoints between treatment groups. Since allocation ratios used to enroll participants may vary between groups during enrollment (eg, participants will be preferentially assigned to Groups 2 and 3 relative to Group 1 after Group 1 has enrolled its first 5 participants), group comparisons will be cautiously interpreted. Moreover, in order to mitigate potential biases, statistical analyses may adjust for potential confounders (eg, age) when comparing endpoints between groups.

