9 STATISTICAL ANALYSIS

This section describes the final study analysis, unblinded as to treatment arm assignment. All data from enrolled participants will be analyzed regardless of how many vaccinations they received. All analyses will be performed using SAS and/or R.

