9.2 Safety Analyses

Reactogenicity: The number and percentage of subjects experiencing each type of reactogenicity sign or symptom will be tabulated by severity. For a given sign or symptom, each subject's reactogenicity will be counted once under the maximum severity for all assessments.

Adverse Events: AEs will be coded into Medical Dictionary for Regulatory Activities (MedDRA) preferred terms. The number and percentage of subjects experiencing each specific AE will be tabulated by severity and relationship to study vaccine. For the calculations in these tables, each subject's AE will be counted once under the maximum severity or strongest recorded causal relationship to treatment. A complete listing of AEs for each subject will provide details including severity, relationship to treatment, onset, duration and outcome.

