10.2 List of Participant Listings

These participant listings are included in the SMB reports:

- Discontinuation Status
- Pregnancies
- Severe or Life-Threatening Local and Systemic Reactogenicities
- Moderate Erythema and Induration
- Expedited Adverse Experiences (EAEs)
- Adverse Experiences of Special Interest (AESIs)
- Severe, Life-Threatening, or Fatal Adverse Experiences
- Adverse Experiences with Relationship to Study Product

- HIV Infection Results from Lab and Reported by Site
- Study Product Administration Errors
- Device Related Adverse Events

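### On-study FNA events have no table of their own and enter the unfiltered AE and MAAE tables, where FNA exposure is confounded with dose group

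*SAP*

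**What the plan says.** SAP 10.1 lists one table for procedure events, "Pre-Enrollment Procedure-Related Events". For AEs in general, SAP 9.2 states: "The number and percentage of subjects experiencing each specific AE will be tabulated by severity and relationship to study vaccine". No relationship-to-procedure category is described. One preferred-term table is restricted by relationship ("Includes Related Experiences Only"). The titles of the body-system, all-severity preferred-term, severe-or-worse preferred-term and MAAE tables carry no such restriction. In SAP 10.2 the nearest listing is "Device Related Adverse Events", but the only device described in SAP 2.4 is the electroporation device.

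FNA is scheduled about three weeks after the second and third DNA doses (Protocol 2.11; Days 50 and 106 in Appendices A and C). Protocol 8.5 requires it in at least half of Groups 2 and 3, and Protocol Section 6 says: "Participants enrolled in Group 1 will not undergo FNA". Protocol 2.13.1 says of FNA: "Can sometimes cause pain, bruising, and bleeding at the site where the needle is inserted", and also names arm numbness or weakness as a rare effect of the local anesthetic. Leukapheresis is done in all participants, at screening and two weeks after the third DNA dose (Protocol 2.12; Day 99 in the appendices).

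All AEs are collected for 30 days after each vaccination. MAAEs are collected beyond that (Protocol 9.1), are reported regardless of relationship (Protocol 8.10), and belong to the first primary objective (Protocol 3.1).

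**The concern.** The plan separates procedure events from vaccine events before enrollment, when no vaccine has been given, but not on study, when the two can be confused. For FNA the mixing is unequal by design: Group 1, the only low-dose group, has no exposure.

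A reader who sets the 0.5 mg column beside the 2 mg columns would see FNA bruising, pain or numbness only at the higher dose, with nothing to show that it followed an axillary procedure. The MAAE table is exposed in the same way. Protocol 8.5 tells participants to contact the site after FNA for severe pain, fever, signs of infection, or arm numbness or weakness, and an unscheduled healthcare visit for any of these meets the MAAE definition. The planned safety analysis is wholly descriptive, so a distortion in the tables is a distortion in the analysis.

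**Working it through.** **1. Timing.** Vaccination 2 is Day 29 and vaccination 3 is Day 85. FNA: 50 − 29 = 21 days and 106 − 85 = 21 days. Second leukapheresis: 99 − 85 = 14 days. All are within 30 days at target. Appendix C allows FNA up to +10 days, so a late one can fall at 21 + 10 = 31 days, just outside.

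**2. The plan's own figures.** No stated figure is challenged. Table 8-1 reproduces by exact binomial in all 20 rows (largest difference 0.005). For example, at a 10% rate the chance of at least one event is 1 − 0.9^9 = 0.61 for n = 9 and 1 − 0.9^18 = 0.85 for n = 18. Those sizes are also the minimum numbers of FNA recipients per group and in Groups 2 and 3 combined.

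**3. Size of the FNA effect.** Inputs:
- f, the share of Groups 2 and 3 aspirated: at least 50% (Protocol 8.5), up to 100%.
- r, the chance that an aspirated participant has a recorded FNA event: not in the documents; assumed 5% to 50%.
- p0, the background any-AE rate, equal in all groups (no true dose effect): assumed 10% or 30%.

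Taking FNA events as independent of background events, Group 1 shows p0, Groups 2 and 3 show p0 + f × r × (1 − p0), and the excess is f × r × (1 − p0). At the low end, 0.5 × 0.05 × 0.9 = 0.0225; at the high end of the first row, 0.5 × 0.5 × 0.9 = 0.225.

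| Excess over Group 1 (points) | r = 5% | 10% | 20% | 30% | 50% |
|---|---|---|---|---|---|
| f = 50%, p0 = 10% | 2.3 | 4.5 | 9.0 | 13.5 | 22.5 |
| f = 50%, p0 = 30% | 1.8 | 3.5 | 7.0 | 10.5 | 17.5 |
| f = 100%, p0 = 10% | 4.5 | 9.0 | 18.0 | 27.0 | 45.0 |
| f = 100%, p0 = 30% | 3.5 | 7.0 | 14.0 | 21.0 | 35.0 |

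For a preferred term that arises only after FNA, Group 1 shows 0% and Groups 2 and 3 show f × r, which is 2.5% to 25% at f = 50%. With 18 recipients, the chance of at least one FNA event is 1 − 0.95^18 = 0.60 at r = 5% and 1 − 0.8^18 = 0.98 at r = 20%.

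**4. Leukapheresis.** Every group has it. With a common event rate q, each group's rate becomes p0 + q × (1 − p0). At q = 39% and p0 = 10% this is 0.10 + 0.39 × 0.90 = 45.1% in all groups, a difference of 0. A true contrast is diluted: 10% against 30% shrinks from 20 points to 20 × (1 − 0.39) = 12.2 points. That is noise, not bias towards either dose.

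**The case against.** The strongest case against is that no planned inference is at stake. SAP 8 sets the safety goal as identifying concerns, with historical controls as reference. The dose comparisons listed in Protocol 6.1.1 are for immunogenicity. SAP 9.2 plans no between-group safety test and does not specify by-group columns; these are only implied by "This section describes the final study analysis, unblinded as to treatment arm assignment". The SAP also names no any-AE table, so the points above describe a summary that a reader would form. All of this stands, and it limits the harm to descriptive reading.

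Vaccine harm also has its own route. The related-only table omits FNA events judged unrelated to vaccine, and the complete AE listing gives relationship and onset. This too stands: that table is affected only through misattribution, which is possible in an open-label trial with aspiration close to the vaccine sites. The unfiltered tables remain mixed.

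Four stronger readings are tempting, and the documents do not support them:
- *The high dose will look less safe.* There is no FNA event rate. Protocol 2.11 reports no significant complications, and Appendix A shows no AE check at the two FNA visits, so minor events may be under-captured.
- *Leukapheresis adds to the dose bias.* It is done in all groups, and its screening round falls within the scope of the pre-enrollment table.
- *About 18 of 45 participants (0.39 × 45 = 17.6) will report paresthesia.* The source of "the most frequent side effect (39%) was paresthesia due to citrate-related hypocalcemia" is a patient study of large-volume collection; its rate need not apply to healthy volunteers here.
- *Transient paresthesia would be read as an AESI.* Appendix I lists immune-mediated neuropathies, and AESIs have a separate listing.

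**Conclusion.** The gap is real and specific to FNA. In every AE or MAAE table not filtered by relationship, FNA exposure is confounded with dose: none in Group 1, at least half of Groups 2 and 3. With no true dose effect, the spurious any-AE excess is about 2 to 23 points at 50% uptake and 10% background, and 4.5 to 45 points at full uptake. Both ranges rest on the assumed 5% to 50% event rate and on complete capture of FNA events. The direction follows from the design; the size is unknown. Group 2 against Group 3 is not systematically affected if FNA uptake is similar in the two. The point concerns how collected events are displayed and is worth correcting because the correction is cheap; it does not undermine a planned test.

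**What to change.** In SAP 10.1, widen the existing procedure table to *Procedure-Related Events (pre- and post-enrollment)*, shown by procedure. Use FNA recipients as the denominator for FNA and the participants undergoing each leukapheresis for that procedure. Show the AE and MAAE tables for Groups 2 and 3 also by FNA status, and keep the all-events tables beside them.

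The split by FNA status needs no attribution judgement. Its limits are small strata (about 9 and 9 per group at minimum uptake, and no unaspirated stratum at full uptake) and self-selection, since FNA is optional. The procedure table does need a judgement on attribution, made open-label. The documents do not show whether relationship to procedure is recorded on study; if it is not, that field is needed.

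The cost is one or two extra tables and a wording change. SAP Section 1 already schedules an update before the first SMB report and before the final analysis. Nothing in clinical conduct changes.

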10.2 List of Participant Listings

These participant listings are included in the SMB reports:

- Discontinuation Status
- Pregnancies
- Severe or Life-Threatening Local and Systemic Reactogenicities
- Moderate Erythema and Induration
- Expedited Adverse Experiences (EAEs)
- Adverse Experiences of Special Interest (AESIs)
- Severe, Life-Threatening, or Fatal Adverse Experiences
- Adverse Experiences with Relationship to Study Product

- HIV Infection Results from Lab and Reported by Site
- Study Product Administration Errors
- Device Related Adverse Events

10.3 List of Figures

These graphs are included in the SMB reports and FSR for Safety:

- Maximum Local Reactogenicities
- Maximum Systemic Reactogenicities
- Boxplots for ALT, Creatinine, Hemoglobin, Platelet Count, AST, WBC, Neutrophil Count, Lymphocyte Count, Monocytes, Eosinophils, Basophils, Atypical lymphocytes

